2.3 Subgroups for Analysis

All of the following subgroup analyses are intended for the primary analysis population. The comparison between the pooled 1-month DAPT arm and the XIENCE V USA historical control will be analyzed descriptively within each quintile for the primary and major secondary endpoints in a specific subgroup. The above quintiles are based on the overall PS, not PS built within each subgroup, as baseline characteristics of subjects are likely to be comparable in each quintile of the overall PS.

2.3.1 Sex

Sex-specific subgroup analyses will be performed on primary analysis population for the primary endpoint and the major secondary endpoints stratified by the overall PS.

2.3.2 Diabetes

Diabetic subgroup analysis will be performed on primary analysis population for the primary and major secondary endpoints stratified by the overall PS. Analyses will be performed within the following subgroups:

- All diabetes mellitus, defined as any diabetics with or without medical treatment
- Non diabetes mellitus.

2.3.3 Covid-19 pandemic impact

In order to assess the COVID-19 impact on the primary endpoint and major secondary endpoint, a descriptive subgroup comparison will be performed on the primary analysis population between subjects whose primary endpoint follow-up overlaps with the pandemic outbreak (such as March 01, 2020 and after) and those whose primary endpoint follow-up is prior to the pandemic outbreak.

2.3.4 Other Subgroups

The following subgroups will be evaluated for the primary analysis population for the primary and major secondary endpoints stratified by the overall PS. Analyses will be performed within the following subgroups:

- Ethnicity (white versus non-white)
- Age (age \geq median vs $<$ median)
- Age \geq 65 years old (US elderly patient)
- Clinical presentation (ACS NSTEMI, ACS unstable angina, non-ACS)

2.4 Analysis Window

- 6 months
- 12 months

2.5 Handling of Missing Data

The primary and major secondary endpoint analyses will be evaluated after propensity score stratification. To handle missing data in propensity score building, multiple imputation method will be performed for baseline characteristics to compute propensity scores from these datasets.

All other analyses will be based on available data with missing data excluded. Any unused or spurious data will be noted as appropriate in the final report.

2.6 Poolability Issue

2.6.1 Multiple Geography Effect

Analysis will be performed by pooling data between XIENCE 28 USA study and XIENCE 28 Global study.

To evaluate the geography/study effect on the primary endpoint, Fisher's exact test will be tested for geography/study effect in the pooled 1-month DAPT arm against an alpha level of 0.15.

If the p-value is < 0.15 , Abbott Vascular will examine subject demographics, baseline clinical, and angiographic characteristics for possible correlations and confounding factors.

2.6.2 Multiple Center Effect

Analysis will be performed by pooling data across study sites.

The pooled 1-month DAPT arm will have a total of approximately 1,600 subjects from approximately 100 sites globally, with a minimum of 640 subjects to a maximum of 800 subjects from approximately 50 sites in the United States and Canada. Subject registration in the XIENCE 28 USA Study is capped at 75 per site. This cap per site will prevent the scenario where the results from a few sites dominate the overall study result. For the analysis of center effect, data from smaller sites may be combined for the analysis. Smaller sites are defined as sites with fewer than 20 subjects per site.

10. **What is the primary purpose of the *Journal of Clinical Endocrinology and Metabolism*?**

11. **What is the primary purpose of the *Journal of Clinical Endocrinology and Metabolism*?**

For more information, contact the Office of the Vice President for Research and Economic Development at [contact] or [contact].

2.7 Adjustments for Covariates

Unless otherwise specified, no adjustments for covariates will be made for any of the variables in the analyses.

2.8 Multiplicity Issues

No multiplicity adjustment is necessary because the tests in this analysis plan are sequential.

2.9 Sensitivity Analysis

The primary and major secondary endpoints between 1-month and 6-month follow-up will be analyzed descriptively for the 1-month clear population removing the patients who do not have antiplatelet medication compliance after 1 month.

For the pooled 1-month DAPT arm, antiplatelet medication non-compliance beyond 1-month follow-up for 1-month clear population is defined as patients who resume P2Y12 inhibitor for more than 7 consecutive days, and/or interrupt aspirin for more than 7 consecutive days between 1-month and 12-month follow up.

In addition, for the 1-month clear population, descriptive comparison between the pooled 1-month DAPT arm and the 3-month DAPT arm from XIENCE 90 Study will be performed for the definite/probable stent thrombosis, death/MI, and BARC 2-5/3-5 bleeding for the time periods of 1-3 month, 1-6 month, and 1-12 month respectively.

In addition, a sensitivity analysis will be performed for the primary endpoint analysis to evaluate the impact of the missing outcome. The analysis will be carried out based on the primary analysis population, and by imputing the missing outcomes for each imputed baseline PS dataset, and Rubin's combination rule [29] will be used to consolidate the final analysis for the 10 duplicates of the imputed dataset. Refer to Appendix A for more details.

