judges that a 3-month DAPT duration, instead of 1-month duration, would be more appropriate for the subject, the physician has the option to transfer the subject to the XIENCE 90 study. This can only occur if the physician is an investigator in XIENCE 90 and if the subject was consented before the procedure. It is also acceptable for the subject to provide consent prior to hospital discharge and up to 3 days after the index procedure, only if the site confirms that the protocol required DAPT regimen is site's standard of care.

[REDACTED]

[REDACTED]

[REDACTED]

[REDACTED]

[REDACTED]

- Subjects who are not “1-month clear” are NOT eligible for P2Y12 inhibitor discontinuation at 1-month. These subjects will be treated per the investigator's discretion and will continue to be followed up through 12 months.

*For prasugrel subjects < 60 kg in weight or \geq 75 years of age, a maintenance dose of 5 mg per day is allowed.

The use of the above antiplatelet medications, including the start and stop date, any changes, as well as the reason to stop, will be documented in the eCRF.

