6.4 Clinical Follow-up for All Subjects

Subjects registered in the trial will receive the following clinical follow-up:

- 1 month (28-35 days): office visit (Note: a formal office visit is required at 1-month follow-up to ensure a thorough clinical evaluation. A telephone contact is an option *only* for subjects who would otherwise be lost to follow-up due to being unable to complete an office visit, but a formal follow-up visit is still preferred at 1-month.)
- 3 months (90 ± 7 days): office visit/telephone contact (office visit is strongly recommended whenever possible)
- 6 months (180 ± 14 days): office visit/telephone contact (office visit is strongly recommended whenever possible)
- 12 months (365 ± 28 days): office visit/telephone contact (office visit is strongly recommended whenever possible)

Clinical follow-up visits should be conducted by the investigator or trial personnel who have been trained to the protocol. At 1-month follow-up visit, the investigator or designee will

[REDACTED]

[REDACTED]

assess whether the subject is “1-month clear” and eligible for P2Y12 inhibitor discontinuation per criteria defined in **Section 6.3.2**.

All registered subjects will be followed up through 12 months, regardless of eligibility to discontinue P2Y12 inhibitor.

The following information will be collected at each of the time points:

- Any adverse events
- Use and compliance of protocol required antiplatelet medication
- Details of any subsequent coronary interventions (e.g., repeat PCI or CABG).

Note that information obtained through indirect contacts with a subject’s healthcare provider or immediate family member will NOT be considered as a trial visit.

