- Type 1: bleeding that is not actionable and does not cause the patient to seek unscheduled performance of studies, hospitalization, or treatment by a healthcare professional; may include episodes leading to self-discontinuation of medical therapy by the patient without consulting a healthcare professional
- Type 2: any overt, actionable sign of hemorrhage (eg, more bleeding than would be expected for a clinical circumstance, including bleeding found by imaging alone) that does not fit the criteria for type 3, 4, or 5 but does meet at least one of the following criteria: (1) requiring nonsurgical, medical intervention by a healthcare professional, (2) leading to hospitalization or increased level of care, or (3) prompting evaluation
- Type 3
 - Type 3a
 - Overt bleeding plus hemoglobin drop of 3 to < 5 g/dL* (provided hemoglobin drop is related to bleed)
 - Any transfusion with overt bleeding
 - Type 3b
 - Overt bleeding plus hemoglobin drop \geq 5 g/dL* (provided hemoglobin drop is related to bleed)
 - Cardiac tamponade
 - Bleeding requiring surgical intervention for control (excluding dental/nasal/skin/hemorrhoid)
 - Bleeding requiring intravenous vasoactive agents
 - Type 3c
 - Intracranial hemorrhage (does not include microbleeds or hemorrhagic transformation, does include intraspinal)
 - Subcategories confirmed by autopsy or imaging or lumbar puncture
 - Intraocular bleed compromising vision
- Type 4: CABG-related bleeding
 - Perioperative intracranial bleeding within 48 h

- Reoperation after closure of sternotomy for the purpose of controlling bleeding
- Transfusion of ≥ 5 U whole blood or packed red blood cells within a 48-h period[†]
- Chest tube output ≥ 2 L within a 24-h period
- Type 5: fatal bleeding
 - Type 5a
 - Probable fatal bleeding; no autopsy or imaging confirmation but clinically suspicious
 - Type 5b
 - Definite fatal bleeding; overt bleeding or autopsy or imaging confirmation

CABG indicates coronary artery bypass graft. Platelet transfusions should be recorded and reported but are not included in these definitions until further information is obtained about the relationship to outcomes. If a CABG-related bleed is not adjudicated as at least a type 3 severity event, it will be classified as not a bleeding event. If a bleeding event occurs with a clear temporal relationship to CABG (ie, within a 48-h time frame) but does not meet type 4 severity criteria, it will be classified as not a bleeding event.

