1.3.1 Selection of Control

The XIENCE V USA historical HBR control is derived based on the following criteria:

Definition of non-complex HBR from XIENCE V USA

- HBR inclusion criteria (any one of the below HBR criteria):
 - Age \geq 75 years
 - History of major bleeding
 - History of stroke
 - Receiving or scheduled to receive chronic anticoagulation therapy
 - Renal insufficiency (creatinine > 2 mg/dl)
 - Anemia (Hb < 11 g/dl or transfusion)
 - Thrombocytopenia (platelet count $< 100.000/\text{mm}^3$)
- Exclusion criteria for non-complex:
 - STEMI
 - LVEF $< 30\%$

- Patients with more than 3 lesions treated during index procedure
- Patients with more than 2 vessels treated during index procedure
- At least one lesion with RVD < 2.25 mm or > 4.25 mm (visual estimation)
- At least one lesion located in left main
- At least one lesion located in graft
- At least one CTO lesion
- At least one in-stent restenosis lesion
- At least one target lesion with length > 32 mm by visual estimation.

The above selection criteria for the XIENCE V USA historical control aligns with the key inclusion/exclusion criteria of the XIENCE 28 USA Study.

For primary analysis, the XIENCE V USA non-complex HBR control subjects must be also 1-month clear, following the same logic as defined for the primary analysis population (refer to Section 1.4).

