1.3.3.2 Other Secondary Endpoint(s)

The following endpoints will be assessed from 1 to 6 months:

- Stent thrombosis (ARC definite/probable, ARC definite)
- All death, cardiac death, vascular death, non-cardiovascular death
- All myocardial infarction (MI) and MI attributed to target vessel (TV-MI, modified ARC)
- Composite of cardiac death or MI (modified ARC)
- Composite of all death or all MI (modified ARC)
- All stroke, ischemic stroke and hemorrhagic stroke
- Clinically-indicated target lesion revascularization (CI-TLR)
- Clinically-indicated target vessel revascularization (CI-TVR)
- Target lesion failure (TLF, composite of cardiac death, TV-MI and CI-TLR)
- Target vessel failure (TVF, composite of cardiac death, TV-MI and CI-TVR)

[figure not shown]
[figure not shown]
- Major bleeding defined by the Bleeding Academic Research Consortium (BARC) type 3-5

The primary endpoint and the major secondary endpoint, as well as all the above secondary endpoints will also be assessed from 6 months to 12 months and from 1 month to 12 months, respectively.

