1.5 Sample Size Calculations

- [REDACTED]
- Sample size:
 - Test arm: a total of ~1,600 subjects pooled from the XIENCE 28 USA Study and the XIENCE 28 Global Study
 - Historical control: ~1400 “1-month clear” subjects from the XIENCE V USA

[REDACTED]

[REDACTED]

[REDACTED]

[REDACTED]

[REDACTED]

[REDACTED]

[REDACTED]

[REDACTED]

[REDACTED]

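### The compliance sensitivity analysis removes whole patients for medication changes up to month 12, whether or not the change came before the 1-6 month event, so its rates can be biased

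*SAP*

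**What the plan says.** SAP 2.9 (Sensitivity Analysis) takes the primary and major secondary endpoints between 1 and 6 months and has them "analyzed descriptively for the 1-month clear population removing the patients who do not have antiplatelet medication compliance after 1 month". It then defines the non-compliant, in the pooled 1-month DAPT arm only, to be "patients who resume P2Y12 inhibitor for more than 7 consecutive days, and/or interrupt aspirin for more than 7 consecutive days between 1-month and 12-month" visits. The unit removed is the patient. No order between medication change and event is specified.

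Other sections bear on this:

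- SAP 1.3.3.2 says the endpoints "will also be assessed from 6 months to 12 months and from 1 month to 12 months, respectively". A month-12 compliance window would fit the 1-12 month versions, but SAP 2.9 applies it to the 1-6 month ones.
- SAP 2.1.5 (Survival Analyses) plans Kaplan-Meier estimates with event-free subjects censored at last contact. It has no censoring at a medication change.
- SAP 1.3.1 says control subjects "must be also 1-month clear, following the same logic as defined for the primary analysis population". No visible text gives the control a compliance rule after month 1.
- Protocol 6.3.2 has the eCRF record start and stop dates, changes and reasons for stopping antiplatelet drugs.

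The SAP is partly redacted, but SAP 2.9 shows no redaction mark. The Appendix A it cites is invoked only for imputing missing outcomes.

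**The concern.** The analysis should show what happened from month 1 to month 6 in patients who kept to the regimen. It instead selects patients on later behaviour that the outcome itself can influence, in two ways.

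1. **Order is ignored.** If an MI is followed by resumption of a P2Y12 inhibitor, or a bleed by interruption of aspirin, the patient and the event both disappear although the patient was compliant when the event occurred. In the other direction, a patient who dies early has little time to be classed non-compliant and so tends to stay in. This second effect needs no event-driven change.
2. **The windows differ.** A change after month 6 cannot affect a 1-6 month endpoint, yet it removes the patient.

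The documents support event-driven changes only indirectly. Under Protocol 6.3.2, freedom from MI in the first month is part of being 1-month clear, and subjects who are not clear are "NOT eligible for P2Y12 inhibitor discontinuation at 1-month". The BARC scale in Protocol Appendix II says type 1 bleeds "may include episodes leading to self-discontinuation of medical therapy by the patient without consulting a healthcare professional". The former subjects are outside this analysis population and type 1 is outside the BARC 2-5 endpoint, so these passages make the mechanism plausible without measuring it. No visible text says how often either occurs after month 1.

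At stake is interpretation: a gap between this rate and the main 1-6 month rate, or agreement between them, could come from the removal rule rather than from compliance.

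**Working it through.** The plan states no figure for this analysis, so there is none to reproduce.

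**Step 1: windows.** Inputs are day 28 for the start (the 1-month visit is at days 28-35), "6 months (180 ± 14 days): office visit/telephone contact", and day 365 for 12 months (Protocol 6.4).

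- Compliance window: 365 − 28 = 337 days.
- Endpoint window: 180 − 28 = 152 days.
- Compliance time after the endpoint closes: 365 − 180 = 185 days; 185/337 = 54.9% (185/330 = 56.1% from day 35).

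This is calendar time, not a measure of bias.

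**Step 2: one deleted event.** SAP 1.5 gives "a total of ~1,600 subjects pooled from the XIENCE 28 USA Study and the XIENCE 28 Global Study". At an assumed 3.5% rate, 56/1600 = 3.50% and 55/1599 = 3.44%, a fall of about 0.06 percentage points. The 1-month-clear subset is smaller and its size is not visible, so the true step is slightly larger.

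**Step 3: rate after removal.** Let r be the true rate, e the share of event patients removed and o the share of event-free patients removed:

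rate = r(1−e) / [r(1−e) + (1−r)(1−o)]

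With r = 3.5% (all three inputs assumed):

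- e = 0.45, o = 0.10: 0.01925/(0.01925 + 0.86850) = 2.17%.
- e = 0.075, o = 0.20: 0.032375/(0.032375 + 0.77200) = 4.02%.
- e = o: 3.50%, no change.

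The bias can go either way and vanishes only when e = o.

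**Step 4: simulation with background changes unrelated to risk.** Assumed over months 1-6: 2.5% death, 2.5% MI and 8% bleeding, with constant hazards and 2,000,000 patients per scenario. Background non-compliance over months 1-12 is 20%. The trigger is the probability that an MI or a bleed itself leads to a qualifying change. Cells are death/MI and BARC 2-5, in percent.

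| Trigger (MI, bleed) | All patients | SAP removal rule | Removal, window ended at month 6 | Censor at a change before the event |
|---|---|---|---|---|
| 0, 0 | 4.94, 7.88 | 5.39, 7.86 | 5.07, 7.88 | 4.94, 7.88 |
| 0.3, 0.3 | 4.92, 7.92 | 4.81, 5.82 | 4.37, 5.67 | 4.91, 7.92 |
| 0.6, 0.5 | 4.94, 7.90 | 4.22, 4.31 | 3.69, 4.13 | 4.94, 7.91 |
| 0.9, 0.8 | 4.92, 7.88 | 3.67, 1.80 | 3.01, 1.67 | 4.93, 7.86 |

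The first row isolates the early-death effect. Shortening the window while still removing whole patients is not a repair.

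**Step 5: wider grid, including conditions unfavourable to censoring.** There were 72 scenarios of 1,000,000 patients, with true death/MI of 3.5% and bleeding of 5%. Varied inputs, all assumed:

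- non-fatal MI as 30 or 60% of death/MI;
- P2Y12 restart after 0, 50 or 90% of MIs;
- aspirin interruption after 0 or 60% of bleeds;
- background non-compliance of 5 or 20% by month 12;
- changes unrelated to risk, or 10% of patients at 5 or 10 times the event and change rates.

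Censoring was placed 8 days after the start of the change. Deaths without a bleed were censored in the bleeding analysis.

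| | Removal | Censoring | Censoring closer to truth |
|---|---|---|---|
| Death/MI | 1.7-4.0% | 3.1-3.5% | 65 of 72 |
| Bleeding | 1.4-5.0% | 4.4-5.0% | 69 of 72 |

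The 3 bleeding exceptions are ties within 0.01 points. The 7 death/MI exceptions all have risk-linked changes. The largest has true 3.51%, removal 3.31% and censoring 3.12%, so censoring is 0.39 − 0.20 = 0.19 points further away.

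**The case against.** The strongest reply is that little depends on this analysis. It is descriptive, with no margin, alpha or success rule attached, and the confirmatory tests in SAP 2.2.1 and 2.2.2 use the whole 1-month-clear population. That stands, and it limits how serious the point is.

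The large shifts also come from assumed trigger probabilities. Without triggers, bleeding is essentially unchanged and death/MI rises (from 4.94% to 5.39% in Step 4), which is unfavourable to the test arm. The count of 65 in 72 describes a chosen grid, not this trial. Both points stand, so the figures illustrate the mechanism and do not predict results.

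The 55% figure might suggest that the late window is the main fault. It is not: in the triggered scenarios of Step 4, ending the window at month 6 moves death/MI further from the truth, because the late removals partly offset the deleted events. The mismatch remains a defect of definition, but correcting it alone is insufficient.

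Finally, censoring has its own assumption, that non-compliance is non-informative, and did worse for death/MI in 7 scenarios. That argues for stating the assumption and reporting counts. It does not rescue a rule that deletes events occurring while the patient was compliant.

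**Conclusion.** The concern holds. Followed exactly, SAP 2.9 can delete endpoint events that themselves caused the medication change, makes early deaths less likely to be removed, and removes patients for behaviour after the endpoint window has closed. No visible text corrects this.

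The window mismatch (185 of 337 nominal days) comes from the documents. The step of about 0.06 points per deleted event combines the SAP's approximate pooled total with an assumed rate. The bias itself cannot be sized or signed from the documents: it depends on how often events prompt changes and on background non-compliance, neither of which is given. The effect is confined to a supportive descriptive analysis. The rule should be changed because a better one is cheap, not because the confirmatory conclusions are at risk.

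**What to change.** In SAP 2.9, replace whole-patient removal with time-ordered censoring, separately for each endpoint:

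- Follow each 1-month-clear subject of the pooled arm from the 1-month visit.
- Count the first event of that endpoint if it occurs before non-compliance is established.
- Otherwise censor on the date the more-than-7-consecutive-day criterion is met, if that date falls within the 1-6 month window.
- Ignore changes after the event or after month 6.
- Report Kaplan-Meier 6-month rates, the number censored, and how many of those changes followed an event of the other endpoint. State how deaths without a bleed are handled in the bleeding analysis.
- If the historical control is shown alongside, state whether it is the full 1-month-clear control or one with a stated adherence rule, and note that a rule applied to one arm only limits the comparison.

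If the removal version is kept, label it as a supplement and state its limitation.

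The cost is SAP wording and programming. The USA eCRF already collects the dates, and Kaplan-Meier with censoring is already in SAP 2.1.5. The Global Study protocol is not among the documents, so its dates are assumed to exist, although the SAP's own 7-day rule for the pooled arm already needs them. The downside is that censoring may be informative when changes follow rising risk or the other endpoint, for example aspirin stopped after a bleed in the death/MI analysis. It reduces the distortion in most of the assumed scenarios, not in all.

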9.2 Analysis Populations

The primary analysis population includes “1-month clear” population, defined as subjects who are free from myocardial infarction (modified ARC), repeat coronary revascularization, stroke, or stent thrombosis (ARC definite/probable) within 1 month (prior to 1-month visit but at least 28 days) after stenting AND have been compliant with 1-month dual antiplatelet therapy (DAPT) without interruption of either aspirin and/or P2Y12 receptor inhibitor for > 7 consecutive days.

If a subject was event-free and DAPT compliant (as defined above) during the first month, but does not stop P2Y12 inhibitor after the 1-month visit, due to physician’s or subject’s decision, this subject will be considered as “1-month not clear”.

[REDACTED]

[REDACTED]

The above defined “1-month clear” population will be pooled from the XIENCE 28 USA Study and XIENCE 28 Global Study for both the primary and major secondary analyses.

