2.1.3 Propensity Score

Given that subjects in the two comparison groups (pooled 1-month DAPT arm vs XIENCE V USA historical control) are not randomized and thus may not have balanced baseline characteristics, the non-inferiority and superiority tests for 1-6 month period will be carried out through stratified analysis in the “1-month clear” population. The stratification will be performed through propensity scores (PS). For each individual a propensity score (i.e., predicted probability between 0 and 1) for group (pooled 1-month DAPT arm) membership will be calculated using logistics regression, with “group” as the outcome and baseline variables including demographic, lesion characteristics, and risk factors as the predictors. Subjects will be categorized into 5 groups based on the calculated propensity scores and their quintiles. Non-inferiority and superiority will then be carried out for the rate of the endpoint using the method described in sections below stratified by the propensity quintiles.

The propensity score modeling and design will be performed by an independent statistician who has no access to any outcome data of the XIENCE 28 USA study, XIENCE 28 Global study and the XIENCE V USA historical control for the integrity and interpretability of study results. The independent statistician will be blinded and have no access to clinical outcome and any follow-up information to avoid introducing bias into the analysis.

Per the recent publication by Yue et al²⁸ on two-stage study designs involving propensity score adjustment, the propensity score calculation results will subsequently be sent to the FDA for review and approval prior to performing the primary endpoint and major secondary endpoint analyses.

2.1.3-1 Propensity Score Variable List

Based on prior clinical experience and clinical research, below is the list of variables that are considered to be related to assignments modeling building:

- Gender
- Age
- Creatinine
- Chronic anticoagulant
- History of stroke
- History of major bleeding
- Platelet
- Hb
- BMI

- Hypertension
- Dyslipidemia
- Prior PCI
- Prior CABG
- Prior MI
- Multivessel disease
- Clinical presentation (ACS (NSTEMI, ACS unstable angina) vs. non-ACS)
- Diabetes
- ACC/AHA lesion complexity
- Total lesion length per patient
- RVD
- Diameter stenosis%
- Bifurcation
- Number of lesions treated
- Number of vessel treated
- Number of stents per patient
- Total stent length per patient
- Discharge P2Y12
- Paris bleeding score

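### The XIENCE 28 versus XIENCE 90 comparison is left unadjusted, although the studies are not randomized against each other and subjects can be transferred between them on physician judgement

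*SAP*

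**What the plan says.** The SAP's section on sensitivity analysis (2.9) plans, for the 1-month clear population, a "descriptive comparison between the pooled 1-month DAPT arm and the 3-month DAPT arm from XIENCE 90 Study will be performed". Three outcomes are covered (definite or probable stent thrombosis; death/MI; bleeding of BARC types 2-5 and 3-5), each over months 1-3, 1-6 and 1-12. It names no stratification or covariate adjustment for this comparison.

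The default in SAP 2.7 is: "Unless otherwise specified, no adjustments for covariates will be made for any of the variables in the analyses". The propensity score in SAP 2.1.3 is motivated by the fact that "subjects in the two comparison groups (pooled 1-month DAPT arm vs XIENCE V USA historical control) are not randomized" and may differ at baseline. It covers that pair of groups only.

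Protocol 6.3.2 opens a route from one compared study to the other. It applies where the investigator "judges that a 3-month DAPT duration, instead of 1-month duration, would be more appropriate for the subject"; such a person may then be moved into XIENCE 90. The physician must also be a XIENCE 90 investigator, and consent conditions apply. The general inclusion criteria (5.3.1.1) place the transfer after the 1-month assessment. Protocol 9.2 adds that an event-free, compliant subject who "does not stop P2Y12 inhibitor after the 1-month visit", by physician or subject choice, is classed as not clear.

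**The concern.** The plan applies a safeguard to one non-randomized comparison and not to the other. The reason SAP 2.1.3 gives for stratifying against XIENCE V USA, possible baseline imbalance, holds equally for XIENCE 90, a separate study with its own enrollment.

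The transfer option adds a specific mechanism. A judgement about how long the subject needs DAPT can take that subject out of the 1-month arm and into the study that supplies the 3-month arm. If those moved have higher ischemic risk, the 1-month rate of death/MI and stent thrombosis falls and the 3-month rate rises with no treatment effect. If they have lower bleeding risk, the bleeding comparison shifts the other way.

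What is at stake is interpretation. This is the only comparison in the visible SAP with another shortened-DAPT study, and it will be read as 1 month against 3 months. Calling it descriptive removes the p-value but not the selection.

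**Working it through.** The plan gives no sample size, margin or expected rate for this comparison, so there is no stated figure to reproduce. The check has two parts.

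**1. Reading the sections together**

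| Question | What the visible text gives |
|---|---|
| Randomized between the two studies? | No; both are separate studies |
| Adjustment specified? | None in SAP 2.9; none by default in SAP 2.7 |
| Does the propensity score cover it? | No; SAP 2.1.3 covers XIENCE V USA only |
| Can subjects move between the compared studies? | Yes, on physician judgement (Protocol 6.3.2) |
| How many are expected to move? | Not stated |
| In which arm are they counted? | Not stated |
| How is 1-month clear applied to XIENCE 90? | Not stated |

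**2. Illustration of what transfer alone could do**

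From the documents: about 1,600 subjects in the pooled 1-month arm (SAP 1.5), of whom up to 800 come from XIENCE 28 USA (SAP 1.3). The remaining 800 are taken as Global.

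Assumed, not in the documents: no true DAPT effect; the same overall risk p in both studies before transfer (4% or 8%); a share f of the transferable subjects moved (1-10%); transferred subjects with RR times the risk of those who stay (2 for ischemic events, 0.5 for bleeding); N90 = 2,000 in XIENCE 90. All 1,600 are treated as otherwise 1-month clear.

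Let NT be the number who could transfer and NO the rest of the pooled arm.

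- Risk among transferable subjects who stay: s = p / (1 - f + f x RR)
- Risk among those moved: RR x s
- 1-month arm: [NT(1 - f)s + NO x p] / [NT(1 - f) + NO]
- XIENCE 90 arm: [N90 x p + f x NT x RR x s] / [N90 + f x NT]

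Worked case: only US subjects transfer (NT = 800, NO = 800), p = 4%, f = 5%, RR = 2.

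- s = 4 / 1.05 = 3.81%; moved subjects 7.62%
- 1-month arm: (760 x 3.81 + 800 x 4) / 1,560 = 3.91%
- XIENCE 90: (2,000 x 4 + 40 x 7.62) / 2,040 = 4.07%
- Apparent difference: -0.16 points

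Difference, 1-month minus 3-month, in percentage points:

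| Who can transfer | RR | p | f = 1% | f = 5% | f = 10% |
|---|---|---|---|---|---|
| US only (800) | 2 | 4% | -0.04 | -0.16 | -0.30 |
| US only (800) | 2 | 8% | -0.07 | -0.33 | -0.60 |
| US only (800) | 0.5 | 4% | +0.02 | +0.09 | +0.17 |
| Both studies (1,600) | 2 | 4% | -0.07 | -0.33 | -0.61 |
| Both studies (1,600) | 0.5 | 4% | +0.04 | +0.18 | +0.35 |

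The visible text does not say whether Global subjects can transfer, so both settings are shown. With N90 = 1,000, the US-only row at RR 2 and p = 4% becomes -0.23 (f = 5%) to -0.41 (f = 10%).

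The worked case also shows what handling transfers achieves. Dropping the 40 moved subjects from XIENCE 90 returns that arm to 4.00% but leaves the 1-month arm at 3.91%, a residual of -0.09. Also counting them in XIENCE 28 gives (760 x 3.81 + 40 x 7.62 + 800 x 4) / 1,600 = 4.00%, a difference of zero.

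**The case against.** The strongest objection is that the comparison is descriptive, carries no test or decision rule, and does not touch the primary or major secondary analysis. SAP 2.2.3 likewise leaves the other secondary endpoints unstratified. This stands, and it limits the severity.

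Second, rules for transferred subjects may exist out of sight. There are redactions directly after the transfer text in Protocol 6.3.2 and after the not-clear rule in 9.2. SAP 1.3 points to two exceptions in Section 1.4, whose visible text breaks off mid-definition. This stands: the absence of a visible rule cannot be called a gap, and a cross-reference in 2.9 would be enough if a rule exists. It does not answer the lack of adjustment, which SAP 2.7 and 2.9 show openly.

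Third, a reader might infer that the 3-month arm passes no filter at 1 month. The documents do not support this. SAP 2.9 restricts the comparison to the 1-month clear population, so some rule may apply to both arms. The requirement to have stopped the P2Y12 inhibitor cannot carry over literally to a 3-month regimen, but how XIENCE 90 subjects are screened is not in these documents.

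Fourth, propensity strata cannot adjust for physician judgement that was not recorded. True, and this is why the transfer versions are needed beside the stratified one. The version that counts transferred subjects in XIENCE 28 includes people whom Protocol 9.2 would class as not clear if they stayed on the P2Y12 inhibitor, so it must be labelled as such.

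**Conclusion.** The point holds in limited form. The XIENCE 90 comparison is non-randomized and crude, and the protocol provides a judgement-based route between the compared studies, so its rates may be confounded.

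A reader might infer that the comparison is biased in favor of 1-month DAPT throughout. The documents do not establish that. The protocol says only that the physician finds 3-month DAPT more appropriate; it gives no risk profile for those moved. The favorable direction is plausible for death/MI and stent thrombosis. For bleeding, moving subjects thought to bleed less would work against 1-month DAPT, as would the XIENCE 28 entry criterion requiring the opinion that bleeding risk beyond 1 month outweighs benefit.

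The size is unknown. On the assumptions above it runs from a few hundredths of a point at 1% transferred to between a sixth and six tenths of a point for ischemic endpoints at 5-10% and a 4% risk. Much larger transfer shares look unlikely: a fifth of a XIENCE 90 arm of 1,000-2,000 would be 200-400 subjects, or 25-50% of an 800-subject US study. Baseline differences between the studies unrelated to transfer are not sized here.

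This is worth correcting because it is cheap, but it does not threaten the trial's main conclusions.

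**What to change.** In SAP 2.9:

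- Add a version stratified by quintiles of a propensity score for XIENCE 28 versus XIENCE 90, using those covariates in list 2.1.3-1 that both studies record and built without access to outcomes. Show it beside the crude comparison.
- Report the number and baseline profile of transferred subjects, and state in which arm they are counted.
- Add two sensitivity versions: one excluding transferred subjects from XIENCE 90, and one that also counts them in XIENCE 28 as registered, labelled as departing from the 1-month clear definition.
- State how 1-month clear is applied to XIENCE 90 subjects.
- State the expected direction of bias separately for ischemic and bleeding endpoints, and note that unrecorded physician judgement remains unadjusted.

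The cost is one more propensity model, outcome-blind work by a statistician, a transfer flag and a few extra tables. No new data collection should be needed, provided XIENCE 90 holds matching baseline fields. The primary and major secondary tests are unaffected.
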